4.2.1.1. Adverse Events of Special Interest

There are no adverse events of special interest identified for this study.

4.2.1.2. COVID-19 Assessment and COVID-19 AEs

The case report form will collect all COVID-19 AEs.

The overall incidence of AEs and SAEs of COVID-19 and COVID-19 AEs leading to study withdrawal will be summarized. The incidence of these events at individual PT level can be obtained from the standard AE/SAE summaries.

4.2.2. Laboratory Data

Summary tables for change from baseline of CD4⁺ T cell counts, haematology and clinical chemistry laboratory tests will be produced. Worst-case post-baseline relative to baseline CCI results will be presented.

Additionally, worst-case (i.e., the highest grade) change in the categories at post-baseline relative to baseline summary table will be provided for CD4⁺ T cell counts and **CCI** based on the cut-off provided in the [Table 1](#) below.

Individual participant plots of the raw values of CD4⁺ T cell counts over time will be presented by study intervention. Line plots of the unadjusted geometric means and corresponding 95% CIs of CD4⁺ T cell counts will be presented over time.

Listings of all Potential Clinical Important abnormalities will be presented for clinical chemistry and haematology (see Section 6.2.1).

Listings of Potential Clinical Important Urinalysis data will be presented. Potential Clinical Important is referred as an increase in Protein or an increase in Occult Blood results, or if microscopy is performed during the study.

Table 1 **Clinically Significant Grades Cut-Offs**

Parameter	Grade	Grade Cut-Off
CD4 ⁺ T Cell Counts	Grade 0	Above $0.5 \times 10^9/L$
	Grade 1	<0.5 to $0.2 \times 10^9/L$
	Grade 2	<0.2 to $0.05 \times 10^9/L$
	Grade 3	Below $0.05 \times 10^9/L$

[1]: Include both absolute and change from baseline values.

[2]: Only absolute values

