7.2.5. Safety Dose Adjustment / Stopping Criteria

The GSK DEC will temporarily halt the study based on the following:

- $CD4^+$ T cell counts below $0.2 \times 10^9/L$ are considered clinically relevant (BHIVA Guidelines Subcommittee, National Cancer Institute - Common Terminology Criteria for Adverse Events (Version 5, NCI-CTCAE) grade 3 or greater) and if sustained for at least 7 days in one participant, this will result in review by the GSK DEC before further participants are dosed.
- **CCI** [REDACTED]
[REDACTED]
[REDACTED]
this will result in review by the GSK DEC before further participants are dosed.
NOTE: **CCI** [REDACTED]
[REDACTED] which, in the opinion of the Investigator, can be reasonably attributed to GSK3888130B.
- **CCI** [REDACTED] are considered clinically relevant (National Cancer Institute - Common Terminology Criteria for Adverse Events (Version 5, NCI-CTCAE) grade 3 or greater). If the **CCI** [REDACTED] in the opinion of the Investigator, can be reasonably attributed to GSK3888130B then this will result in review by the GSK DEC before further participants are dosed.
- Clinically significant [National Cancer Institute - Common Terminology Criteria for Adverse Events (Version 5, NCI-CTCAE) grade 3 or greater] infusion reactions occurring in one participant.
- As a result of review of safety data at the end of each cohort.
- If one or more participants from any dose level experiences a Serious Adverse Event (SAE) which has a reasonable possibility of relation to GSK3888130B, no further participants will be dosed until a full safety review of the data has taken place.
- If two or more participants in the same cohort experience a 'severe' non-serious adverse reactions which has a reasonable possibility of relation to GSK3888130B, no further participants will be dosed until a full safety review of the data has taken place. 'Severe' non-serious adverse reactions can be either within or not within the same system organ class.

In the event of reaching the stopping criteria, the dose escalation will stop, and no further participants will be dosed. If after consultation the Sponsor deems that dosing can resume at that level or higher the Sponsor will submit an application for a substantial amendment to the Regulatory Agency to present the data and approve a revision to the protocol.

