8.2.2. Vital Signs

- Tympanic temperature, pulse rate, respiratory rate, and blood pressure will be assessed.

- Blood pressure and pulse measurements will be assessed semi-supine with a completely automated device. Manual techniques will be used only if an automated device is not available.
- Blood pressure and pulse measurements should be preceded by at least 5 minutes of rest for the participant in a quiet setting without distractions (e.g., television, mobile phones).
- Vital signs (to be taken before blood collection for laboratory tests) will consist of three pulse and three blood pressure measurements (3 consecutive blood pressure readings will be recorded at intervals of at least 1 minute).

8.2.3. **Electrocardiograms**

- Triplicate and single 12-lead ECGs will be obtained as outlined in the SoA (see Section 1.3) using an ECG machine that automatically calculates the heart rate and measures PR, QRS, QT, and QTc intervals.
- If triplicate ECG are required, 3 individual ECG tracings should be obtained as closely as possible in succession, but no more than 2 minutes apart.
- Use of Fridericia's formula (QTcF) is preferred in this study. The formula may not be changed or substituted once the participant has been enrolled. Safety ECGs and other non-protocol specified ECGs are an exception.

8.2.4. **CCI**

- **CCI**
- **CCI**
- **CCI**
- **CCI** will be captured as outlined in the SoA [Section 1.3].

8.2.5. **Clinical Safety Laboratory Assessments**

- See [Appendix 2](#) for the list of clinical laboratory tests to be performed and to the SoA for the timing and frequency.
- The Investigator must review the laboratory report, document this review, and record any clinically significant changes occurring during the study as an AE. The laboratory reports must be filed with the source documents.
- All laboratory tests with abnormal values (above or below the normal range) during participation in the study should be repeated until the values return to normal or baseline or are not considered clinically significant by the Investigator or Medical Monitor.
 - If clinically significant values do not return to normal/baseline within a period of time judged reasonable by the Investigator, the etiology should be identified and the sponsor notified.
- All protocol-required laboratory tests, as defined in Section 10.2, must be conducted in accordance with the laboratory manual and the SoA (Section 1.3).

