1.1. Objectives and Endpoints

Objectives	Endpoints
Primary	
To investigate the safety and tolerability of single IV and SC doses of GSK3888130B in healthy participants.	
 • Occurrence of Adverse Events (AEs) and Serious Adverse Events (SAEs). • Occurrence of clinically significant changes in laboratory values (CD4⁺ T cell counts, haematology, chemistry, urinalysis and virology), vital signs and 12lead electrocardiogram (ECG) readings.
Secondary	
To characterise the serum PK profile of single IV or single SC doses of GSK3888130B in healthy participants.	Serum concentrations of GSK3888130B and derived PK parameters as data permit, including area under the concentration-time curve [AUC], maximum concentration [Cmax], time to Cmax [Tmax], half-life [t _{1/2}], clearance [CL].
To evaluate the immunogenicity of single doses of GSK3888130B in healthy participants.	Incidence of Anti-Drug Antibodies (ADAs) against GSK3888130B.
To characterise the effects of GSK3888130B on target engagement (TE).	Change from baseline in derived free IL-7 levels (calculated from total IL-7 assay measurements) over time.
To characterise the effect of single doses of GSK3888130B on PD biomarker Bcl-2.	Change from baseline in T cell Bcl-2, measured in blood over time.
Tertiary/Exploratory/Other	
CCI	

Objectives	Endpoints
CCI	

Objectives	Endpoints
CCI	

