4.2.1. Adverse Events

An adverse event (AE) is considered study intervention emergent if the AE onset date is on or after study intervention start date. All AE summaries will be based on study intervention emergent events unless otherwise specified. SAE summaries will be based on all SAEs reported regardless of whether they meet the definition of study intervention emergent or not. All AE and SAE summaries will be by System Organ Class (SOC) and Preferred Terms (PT) or only by PT, unless otherwise specified.

Adverse events will be coded using the standard Medical Dictionary for Regulatory Affairs (MedDRA dictionary) and graded by the investigator according to the National Cancer Institute - Common Terminology Criteria for Adverse Events (NCI-CTCAE, version 5).

An overview summary of AEs, including counts and percentages of participants, will be summarized for the following categories and subcategories.

- AE
 - Any AEs
 - AEs related to study intervention
 - AEs leading to study withdrawal
- SAE
 - Any SAEs
 - SAEs related to study intervention

A study intervention-related AE/SAE is defined as an AE for which the investigator classifies the possible relationship to study intervention as “Yes”. If relationship to study intervention is missing then worst-case approach will be applied (i.e. missing will be handled in the same way as ‘Yes’).

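### SAP Table 1 labels CD4+ counts of 0.05 to <0.2 x10^9/L as Grade 2, but Protocol 7.2.5 classes every count below 0.2 as NCI-CTCAE v5 grade 3 or greater

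*SAP*

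**What the plan says.** Protocol 7.2.5 sets the CD4+ criterion for a temporary halt. It states that "T cell counts below $0.2 \times 10^9/L$ are considered clinically relevant" and supports this with a parenthesis citing "BHIVA Guidelines Subcommittee, National Cancer Institute - Common Terminology Criteria for Adverse Events (Version 5, NCI-CTCAE) grade 3 or greater". A count below 0.2 x10^9/L sustained for at least 7 days in one participant then triggers review by the dose escalation committee before anyone else is dosed.

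SAP 4.2.2 plans a categorical summary of the same variable: "Additionally, worst-case (i.e., the highest grade) change in the categories at post-baseline relative to baseline summary table will be provided". The categories come from Table 1:

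- Grade 0: "Above $0.5 \times 10^9/L"
- Grade 1: from <0.5 down to 0.2 x10^9/L
- Grade 2: "<0.2 to $0.05 \times 10^9/L"
- Grade 3: below 0.05 x10^9/L

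The visible text of Table 1 names no grading system. The only one named in the visible SAP is in section 4.2.1, where adverse events are to be "graded by the investigator according to the National Cancer Institute - Common Terminology Criteria for Adverse Events (NCI-CTCAE, version 5").

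SAP 1.1 lists as a primary endpoint "Occurrence of clinically significant changes in laboratory values (CD4⁺ T cell counts, haematology, chemistry, urinalysis and virology"), together with vital signs and ECG readings.

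**The concern.** The two documents give different grade numbers to the same CD4+ count. With NCI-CTCAE v5 the only scale named in the visible SAP, a reader can take the Table 1 grades as CTCAE grades. Someone looking for Grade 3 in the shift table would then find only counts below 0.05 x10^9/L, while the protocol's grade 3 or greater covers everything below 0.2.

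This matters because low CD4+ counts are a central safety question here. Infection and lymphopenia are listed as a risk in Protocol 2.3.1, and CD4+ count is the first laboratory value named in the primary endpoint. The shift table is also the only categorical CD4+ summary in the visible SAP: the ranges for potential clinical importance in SAP 6.2.2 include lymphocytes but not CD4+. Under SAP 6.2.4, unscheduled visits are left out of by-visit displays but do enter worst-case derivations. A low count found at an extra visit would therefore reach a summary table through the worst-case category.

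One count might also carry two grades in the same report. Protocol 8.2.5 requires the investigator to "record any clinically significant changes occurring during the study as an AE", and SAP 4.2.1 grades adverse events by CTCAE v5.

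**Working it through.** No sample size, power or error-rate figure lies behind this point, so there is no plan figure to reproduce. The check applies both documents' rules to the same counts (all in x10^9/L).

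**Inputs.** SAP Table 1 bands: >0.5, 0.2 to <0.5, 0.05 to <0.2, and <0.05. Protocol 7.2.5: counts <0.2 are grade 3 or greater; no grade is given at or above 0.2.

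**Band by band.**

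| CD4+ count | Protocol 7.2.5 | SAP Table 1 | Result |
|---|---|---|---|
| <0.05 | grade 3 or greater | Grade 3 | compatible |
| 0.05 to <0.2 | grade 3 or greater | Grade 2 | conflict, at least 3 − 2 = 1 grade |
| 0.2 to <0.5 | no grade given | Grade 1 | no conflict shown |
| exactly 0.5 | no grade given | none | ungraded |
| >0.5 | no grade given | Grade 0 | no conflict shown |

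One of the four bands conflicts.

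**Grid check.** Both rules were applied to counts from 0.00 to 1.20 in steps of 0.01. Of the 20 values below 0.2, 15 (0.05 to 0.19) are Grade 2 in the SAP and 5 (0.00 to 0.04) are Grade 3. None of the 20 is ungraded. The set with SAP Grade 2 or 3 is identical to the set below 0.2. The only ungraded value on the whole grid is 0.5. These are counts of grid points, not a forecast of how many participants would be affected.

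**Effect on the display.** In an eight-person cohort randomised 3:1, 8 × 3/4 = 6 participants receive active drug. Assume, purely for illustration, that one of them has a worst count of 0.15.

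- Shift table under SAP Table 1: Grade 2 = 1/6 = 16.7%; Grade 3 = 0/6.
- Protocol classification: grade 3 or greater = 1/6 = 16.7%.
- Participants below 0.2: 1/6 under either (SAP Grades 2 + 3 = 1 + 0).

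The label changes; the number below 0.2 does not.

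**The case against.** The strongest reply is that this is a drafting matter. Both documents cut at 0.2, so nobody below that threshold disappears from the table. Individual plots of raw CD4+ values are planned. The halt rule works on the absolute count. No hypothesis is tested, and no estimate or analysis set depends on the grade number. Protocol 9.4.3 makes the investigator's attribution of adverse events the principal consideration in interpreting safety. For dose escalation, SAP 4.6 has the site supply the CD4+ counts. All of this is correct, and it limits the consequence to the label.

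A second reply is that Table 1 may not be a CTCAE scale at all. It runs from 0 to 3 and stops there, whereas the protocol's wording implies levels above 3, and SAP 4.2.1 invokes CTCAE for events graded by the investigator rather than for programmed laboratory categories. Part of SAP 4.2.2 is redacted, and display details sit in the Output and Programming Specification, which is not available here. A source could be stated in either place. This possibility stands. It would not remove the problem: an unlabelled grade that differs from the protocol's grade for the same count would still need a name or a different set of labels.

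A third reply is that two grades for one count in a single report is speculative. The investigator would have to record the count as an adverse event, and an output would have to show its grade; SAP 4.2.1 describes no by-grade table. That is fair, and the possibility carries little weight in the conclusion.

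**Conclusion.** The conflict is real and should be corrected. Counts from 0.05 to <0.2 x10^9/L are Grade 2 in SAP Table 1 and grade 3 or greater in Protocol 7.2.5: one band of four, by at least one grade. Followed as written, the plan would report these counts under a lower grade than the protocol assigns, in a display that supports a named component of the primary safety endpoint.

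No participant below 0.2 is lost because of the mislabelling, and no halt or monitoring decision changes. The gap at exactly 0.5 is a separate and smaller boundary slip; a baseline or worst value there would have no row in the table.

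The conclusion rests on the visible text alone. The documents do not reproduce the CTCAE criteria, so they cannot show which label is right, and a study-specific scale for Table 1 cannot be excluded.

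**What to change.** Check the labels in SAP Table 1 and Protocol 7.2.5 against the grading source the protocol cites, and reconcile them so that a given count has the same grade in both. If Table 1 is meant as a study-specific scale, say so and rename its levels, for example as count bands, so that they cannot be read as CTCAE grades.

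In either case, name the source beneath the table, keep the boundary at 0.2 so that the number of participants below it can be read off directly, and assign a count of exactly 0.5 to a category. No change to any halt or monitoring rule is implied.

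The cost is one table edit or footnote in the SAP and one programming format. No new data are needed.

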4.2.2.1. Virology Data

Virology data includes both quantitative and qualitative data as shown in [Table 2](#). Appropriate summary tables (for quantitative data, these will be based on continuous untransformed data) will be provided (see Section [4.1.1](#)).

Table 2 Virology Data

Biomarker	Result	Classification
Serology (Immunology as per SDTM data standards)		
CMV IgG (AU/mL)	Quantitative Result	<6.0 is Non-reactive >= 6.0 is Reactive
CMV IgM	Qualitative Result	Positive/Negative
EBNA IgG (U/mL)	Quantitative Result	< 5 U/mL is Negative
VCA IgG (U/mL)	Quantitative Result	< 20 U/mL is Negative
EBV VCA ab (IgM) (U/mL)	Quantitative Result	< 20 U/mL is Negative
Varicella Zoster IgG (mIU/mL)	Quantitative Result	<150 mIU/mL is Negative
Varicella Zoster IgM	Qualitative Result	Positive/Negative
Viral quantification		
EBV (Copies/mL)	Quantitative Result	N/A
CMV (Copies/mL)	Quantitative Result	N/A
Varicella	Qualitative Result	Positive/Negative

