	
[REDACTED] CCI [REDACTED] CCI [REDACTED]
 
[REDACTED]. Pre-clinical experience with healthy cynomolgus monkeys, as well as internal experience with a monoclonal antibody to the IL-7R (GSK2618960) in two Phase 1 HV studies (NCT01808482 and NCT022931610) [Ellis, 2019], indicate that after single doses of anti-IL-7R mAb there were minimal changes on T cell subsets and absolute lymphocyte counts respectively, which were also transient. An excess of infections was not reported in these studies; only nasopharyngitis was observed in 17% and 50% of participants on anti-IL-7R mAb for studies I7R116702 and 200902, respectively. Baseline serology (EBV, HIV, HepB, HepC, HSV, CMV, VZV) was stored for analysis and comparison if symptoms of viral infection occurred (Study I7R116702), and serology analysed (EBV and CMV) only if participants had alanine amino transferase (ALT) $>3\times\text{ULN}$ (Study 200902). There were no reports of viral infection, therefore virology samples were not analysed. Across both studies, no deaths, SAEs or other significant AEs were reported. No AEs led to study withdrawal.
 
In a 12-week repeat dose study (different regimens), with an anti-IL-7R mAb [Herold, 2019], there was a significant decline over the dosing period in CD4$^{+}$ and CD8$^{+}$ effector and central memory T cells and CD4$^{+}$ naive cells, but there were fewer effects on CD8$^{+}$ naive T cells. Only a small decline in these cells was noted after the first dose of each regimen. All dosing regimens had receptor occupancy $>90\%$. Serum was collected for EBV and cytomegalovirus (CMV) IgG antibodies and viral deoxyribonucleic acid (DNA) at baseline, on day 85 and at the end of follow-up. Four participants seroconverted from negative EBV IgG before treatment to positive IgG antibody. Two of these participants had EBV symptoms. One participant who was negative at baseline for CMV viral DNA but positive for IgG antibody, had detectable viral DNA on day 85 (asymptomatic), returning to negativity by day 127.
 
Recombinant IL-7 cytokine was currently being trialled (InterLeukin-7 [CYT107] To Improve Clinical Outcomes in Lymphopenic Patients with COVID-19 Infection UK Cohort [ILIAD-7-UK]; NCT04379076) to improve clinical outcomes in lymphopenic patients with SARS-CoV-2 infection. The study was terminated in April 2022 due to poor accrual. There are no publicly available results from this study.
	
During the ongoing SARS-CoV-2 infection risk:
 
Inclusion: participants must complete a two-dose SARS-CoV-2 vaccination schedule and adhere to travel restrictions.
 
Exclusion: participants with recent SARS-CoV-2 positive contacts.
 
Temporary Halt Criteria:
 
 1. CD4$^{+}$ T cell counts below $0.2\times 10^9/\text{L}$ sustained for at least 7 days in 1 participant will result in review by the GSK DEC before further participants are dosed. 2. SARS-CoV-2 infection risk data are evolving. SARS-CoV-2 infection data in the UK and specifically local area data in the vicinity of the Phase 1 unit where the study will be conducted will be monitored. In the event of an increase in SARS-CoV-2 infection rates, with resultant increase in moderate to severe COVID-19, that cannot be managed through two-dose vaccination regimens available at the time of the study (e.g. new variants), the study will be temporarily halted. 
Participant counselling: See Appendix 6

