3. OBJECTIVES AND ENDPOINTS

Objectives	Endpoints
Primary	

 To investigate the safety and tolerability of single IV and SC doses of GSK3888130B in healthy participants. 	
 Occurrence of Adverse Events (AEs) and Serious Adverse Events (SAEs). Occurrence of clinically significant changes in laboratory values (CD4⁺ T cell counts, haematology, chemistry, urinalysis and virology), vital signs and 12-lead electrocardiogram (ECG) readings.
Secondary	

 To characterise the serum PK profile of single IV or single SC doses of GSK3888130B in healthy participants. 	
 Serum concentrations of GSK3888130B and derived PK parameters as data permit, including: area under the concentration-time curve [AUC], maximum concentration [Cmax], time to Cmax [Tmax], half-life [t_{1/2}], clearance [CL].

 To evaluate the immunogenicity of single doses of GSK3888130B in healthy participants. 	
 Incidence of Anti-Drug Antibodies (ADAs) against GSK3888130B.

 To characterise the effects of GSK3888130B on target engagement (TE). 	
 Change from baseline in CCI [REDACTED] [REDACTED] over time.

Objectives	Endpoints

• To characterise the effect of single doses of GSK3888130B on PD biomarker Bcl-2.	
• Change from baseline in T cell Bcl-2, measured in blood over time.

Objectives	Endpoints
CCI	

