[REDACTED]. The two SC dose levels will provide information on GSK3888130B CCI [REDACTED], which might be dose-dependent. The IV route of administration was selected for the initial dosed cohorts to enable monitoring of early safety signals during infusion. SC cohorts are interspersed with IV cohorts to minimise the number of subjects who are exposed to GSK3888130B. The dose escalations have been planned to ensure that exposure increments remain consistent between ascending dose levels/cohorts based on PK exposure predicted from pre-clinical data (see Section 4.3.2).

To ensure unbiased outcomes, a double-blind approach will be used, with the participants, Investigator and Clinical Unit staff all blind to treatment allocation.

CCI [REDACTED]
[REDACTED]
[REDACTED]
[REDACTED]
[REDACTED]
[REDACTED] CCI [REDACTED]
[REDACTED]

[REDACTED]

As GSK3888130B potently neutralises IL-7 and is therefore anticipated to impact T cell development, differentiation and function (including memory T cell responses), GSK3888130B has the potential to increase the risk of infection.

Previous clinical experience with an anti-IL-7R mAb antagonist GSK2618960 in two Phase 1 studies (NCT01808482 and NCT022931610) in 24 healthy participants, reported no viral infections [Ellis, 2019] and [REDACTED]

In a Phase 2b, 12-week repeat-dose escalation study (NCT02038764) evaluating IL-7R blockade with RN168 (a humanised IgG1 mAb which binds to IL-7RA (CD127)), in 37 subjects with type 1 diabetes, four participants seroconverted from negative Epstein-Barr Virus (EBV) IgG before treatment to positive IgG antibody response following dosing. Two of these participants had symptomatic EBV infection [Herold, 2019]. In this repeat dose study, between 90% and 100% IL-7R occupancy and near-complete inhibition of pSTAT5 (IL-7R downstream signaling) was observed at all dose levels and regimens tested.

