Prevalence of viral infections in the community are generally considered to be of low-risk in the UK due to high childhood vaccination uptake (with the exception of the recent SARS-CoV-2 pandemic). Therefore, in the absence of viral infections in healthy volunteer studies with an anti-IL-7R GSK2618960, preclinical toxicity study with GSK3888130B and risk mitigation plans within this study (detailed in Section 2.3.1), the risk to healthy volunteers from a single dose of GSK3888130B is considered to be very low. In addition, baseline, midpoint, and end of study viral samples will be drawn and analysed for EBV, CMV and VZV infection in order to characterize the infection risk (including asymptomatic infection) and determine trends to inform future clinical development.

Severe Acute Respiratory Syndrome-Coronavirus-2 (SARs-CoV-2) vaccination and UK Government policies have seen the risk of severe Coronavirus 19 (COVID-19) disease reduced in the general population in the UK. However, it is noted that the greatest impact of IL-7R inhibition has been shown to be on the central and effector memory T cell response/cell number [Herold, 2019]. While these cell populations drive the autoimmune response in disease, they are also important in mounting a T cell mediated memory

response to infections and inhibition of IL-7 may reduce this response. Evidence suggests that the current approved SARS-CoV-2 vaccines are protective largely due to the B-cell antibody response, as efficacy correlates with antibody titres and their neutralising capacity [Earle, 2021]. Therefore, participants will be required to have been fully vaccinated for SARS-CoV2 vaccines (two-dose regimen) 30 days prior to dosing, as efficacy of these vaccines are reported to give substantial protection against hospitalisation from current SARS-CoV-2 strains.

As social contact returns to pre-pandemic norms there is likely to be a resurgence in influenza activity in winter 2022 to 2023 to levels similar to or higher than before the pandemic [Gov.UK. National flu immunisation programme, 2022]. Therefore, all participants recruited into the study to be dosed within the influenza season (1st October to the 30th April) will be required to be vaccinated with an approved seasonal influenza vaccine.

CCI [REDACTED]
[REDACTED]
[REDACTED]

12-lead ECGs will be routinely performed in both IV and SC cohorts to provide contemporaneous safety analysis and data for the primary outcome.

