10.2. Appendix 2: Clinical Laboratory Tests

The tests detailed in [Table 1](#) will be performed by the local laboratory.

Protocol-specific requirements for inclusion or exclusion of participants are detailed in [Section 5](#) of the protocol.

Additional tests may be performed at any time during the study as determined necessary by the Investigator or required by local regulations.

Table 1 Protocol-Required Safety Laboratory Tests

Laboratory Assessments	Parameters			
Haematology	Platelet Count	RBC Indices: MCV MCH %Reticulocytes	WBC count with Differential: Neutrophils Lymphocytes Monocytes Eosinophils Basophils	
	RBC Count			
	Haemoglobin			
	Haematocrit			
	CD4 ⁺ T cell Count	CCI [REDACTED]		
Clinical Chemistry ¹	Urea/BUN	Potassium	Aspartate Aminotransferase (AST)/ Serum Glutamic-Oxaloacetic Transaminase (SGOT)	Total and direct bilirubin
	Creatinine	Sodium	Alanine Aminotransferase (ALT)/ Serum Glutamic-Pyruvic Transaminase (SGPT)	Total Protein
	Glucose (non-fasting)	Calcium	Alkaline phosphatase ²	
	CCI [REDACTED] [REDACTED] [REDACTED]	CCI [REDACTED]		
Routine Urinalysis	
 Specific gravity pH, glucose, protein, blood, ketones, bilirubin, urobilinogen, nitrite, leukocyte esterase by dipstick Microscopic examination (if blood or protein is abnormal, or if any other trace is detected) 			

Laboratory Assessments	Parameters
	
 • CCI ██████████ described in SRM
Viral quantification and serology	
 • EBV, CMV and VZV. • SARS-CoV-2 (serology only)
Other Screening Tests	
 i. Follicle-stimulating hormone and oestradiol (as needed in women of non-childbearing potential only) ii. Alcohol and drug screen (to include at minimum: amphetamines, barbiturates, cocaine, opiates, cannabinoids and benzodiazepines) iii. Serology (HIV antibody, hepatitis B surface antigen [HBsAg], hepatitis B core antibody and hepatitis C virus antibody and hepatitis C RNA) iv. Mycobacterium tuberculosis QuantiFERON Gold v. SARS-CoV-2 testing (performed as per site local procedures) vi. Smoking breath test

NOTES:

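### SAP 4.2.2.1 does not count participants who go from negative to positive on virology, so conversions not recorded as adverse events are missed

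*SAP*

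**What the plan says.** Protocol Section 3 includes virology in the primary safety endpoint, "Occurrence of clinically significant changes in laboratory values". Protocol 4.2 gives the reason for drawing EBV, CMV and VZV samples at baseline, midpoint and end of study: "in order to characterize the infection risk (including asymptomatic infection) and determine trends to inform future clinical development".

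SAP 4.2.2.1 refers virology to the general summaries of SAP 4.1.1 and adds that "for quantitative data, these will be based on continuous untransformed data". Under SAP 4.1.1, continuous untransformed data get at least n, mean, 95% CI, SD, median, minimum and maximum, with the number of zeros as an optional extra. Categorical data get the number and percentage in each category. Table 2 of SAP 4.2.2.1 lists ten assays and prints a cut-off for five quantitative serology assays. For EBV and CMV copies/mL the classification is N/A.

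Virology appears in Protocol 10.2 among the "Protocol-Required Safety Laboratory Tests". Under Protocol 8.2.5 the investigator must "record any clinically significant changes occurring during the study as an AE", and SAP 4.2.1 then provides "An overview summary of AEs, including counts and percentages of participants".

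**The concern.** Infection is a named risk of blocking IL-7. The protocol describes its closest precedent, a 12-week repeat-dose study of an anti-IL-7 receptor antibody, as counts of participants. Protocol 2.3.1 reports that "Four participants seroconverted from negative EBV IgG before treatment to positive IgG antibody", and that one participant had newly detectable CMV DNA without symptoms. Protocol 4.2 gives the study size: "in 37 subjects with type 1 diabetes, four participants seroconverted".

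A reader of this trial's report will want the same kind of count: how many participants who were negative at baseline became positive, on each dose and on placebo. Group summaries by visit can show a trend, but they do not reliably show who crossed from negative to positive. The adverse event tables count changes judged clinically significant, with or without symptoms. They would miss, for example, a seroconversion judged not clinically significant, which bears on the asymptomatic infection that the protocol says it wants to characterise.

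**Working it through.** The plan states no figure to reproduce here. The check traces each assay to its summary, looks for a baseline-paired rule elsewhere, and then tests whether the planned statistics could recover the count.

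**Step 1. The ten assays in SAP Table 2**

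| Assays | Number | Summary under SAP 4.1.1 | Cut-off in Table 2 | Baseline-to-post rule |
|---|---|---|---|---|
| CMV IgG, EBNA IgG, VCA IgG, EBV VCA IgM, VZV IgG | 5 | Continuous | Yes | None readable |
| EBV and CMV copies/mL | 2 | Continuous | N/A | None readable |
| CMV IgM, VZV IgM, varicella | 3 | n (%) per category | Positive/negative | None readable |

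**Step 2. Other places where the rule might stand**

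- SAP 4.1.3.1 defines change from baseline. SAP 4.2.2 names CD4+ counts, haematology and chemistry for such tables, not virology.
- SAP 6.2.4 adds a worst-case post-baseline row and lists unscheduled visits. It does not pair that row with the participant's baseline.
- The readable criteria in SAP 6.2.2 contain no virology.
- Other endpoints do get participant-level tables: baseline-relative categories for CD4+ (SAP 4.2.2) and QTcF (SAP 4.2.4), and incidence for anti-drug antibodies (SAP 4.3.2).

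**Step 3. Can the planned statistics recover the count?** All values below are assumed. Six participants on one dose corresponds to 8 × 3/4 in a 3:1 cohort. Intervals for proportions are exact (Clopper-Pearson) 95%.

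*Illustration 1: VCA IgG, negative below 20 U/mL.* Baseline is (5, 8, 90, 110, 200, 400), with mean 813/6 = 135.5. Two participants are at risk.

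| | Seroconversion, 8 to 60 | Seropositive rise, 200 to 252 |
|---|---|---|
| Mean | 865/6 = 144.2 | 865/6 = 144.2 |
| Median; minimum; maximum | 100; 5; 400 | 100; 5; 400 |
| SD (95% CI of mean) | 140.8 (-3.6 to 291.9) | 154.3 (-17.8 to 306.1) |
| Change: mean; SD; median; min; max | 8.7; 21.2; 0; 0; 52 | 8.7; 21.2; 0; 0; 52 |
| New positives among those at risk | 1/2 (1.3% to 98.7%) | 0/2 (0 to 84.2%) |

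The changes are one +52 and five zeros in both columns, so the mean is 52/6 = 8.7 and the SD is 52/√6 = 21.2. Only the absolute SD and CI differ, and neither identifies a conversion. The result is the same over a range of seroconverted values:

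| Post-dose value (matched rise) | Mean change, both | Absolute SD: seroconversion / rise |
|---|---|---|
| 20 (12) | 2.0 | 146.4 / 149.5 |
| 40 (32) | 5.3 | 143.4 / 151.7 |
| 60 (52) | 8.7 | 140.8 / 154.3 |
| 80 (72) | 12.0 | 138.6 / 157.3 |

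*Illustration 2: viral load.* Baseline is (0, 0, 0, 0, 0, X). Post-baseline is either unchanged or (0, 0, 0, 0, X, 0). The two sets hold the same values, so every absolute statistic, including the number of zeros, agrees for any X. Change from baseline, if tabulated, separates them: SD 0 against √(2X²/5) = 0.632X, and maximum 0 against X. New viraemia among those at risk is 0/5 (0 to 52.2%) or 1/5 (0.5% to 71.6%). If nobody is viraemic at baseline, the maximum shows a new case, and the number of zeros, if tabulated, gives the count.

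*Illustration 3: qualitative assay.* With 1/6 positive at baseline and 1/6 later, the positive participant may be the same person (0/5 new) or a different one (1/5 new). The n (%) by visit is identical.

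**The case against.** The strongest reply is that the rule may exist in text we cannot read. SAP 4.2.4 leaves full details of the safety displays to the OPS. Protocol 9.4.3 refers to the sponsor's display standard. SAP 4.2.2 has redacted items in its baseline-relative sentences. This stands as a limit on the conclusion: the finding concerns the readable SAP only.

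SAP 4.1.1 also gives its statistics as a minimum, and the classification column in Table 2 could be meant to produce n (%). That is possible, but the text does not say so, and n (%) by visit would still not be paired with baseline.

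Clinically significant changes reach the adverse event tables, and the adverse event definition in Protocol 10.3.1 also covers newly diagnosed conditions. So the primary endpoint as worded is not lost. This is right. What is left uncounted is changes not recorded as adverse events, some of which fall within the purpose stated in Protocol 4.2.

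The comparators are imperfect. Anti-drug antibody incidence has no stated baseline pairing, and CD4+ and QTcF also serve as triggers for committee review. The omission is therefore better judged against the purpose of the virology samples than as an inconsistency.

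Finally, the examples are constructed, and in some datasets the planned statistics would reveal a case. With a single baseline-negative participant, the minimum would itself cross the cut-off. The examples show that the count cannot be relied on, not that it is always hidden. The groups are small and no hypothesis is tested, so the added tables would be descriptive.

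**Conclusion.** The concern holds. In the readable SAP, none of the ten virology assays has a rule that turns baseline-negative to post-baseline-positive into a count of participants. For EBV and CMV load there is not even a classification to apply. Followed as written, the plan gives group summaries that can be the same, or differ only in SD and CI, whether or not a conversion occurred: 1/2 against 0/2 at risk in the IgG example, and 1/5 against 0/5 in the qualitative one.

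The gap covers only changes not recorded as adverse events, and the numerical examples rest on assumed values. The protocol does not give the number EBV-negative at baseline in the precedent study, and that study's repeat-dose rate does not carry over to a single dose, so no expected number of conversions is claimed. Confidence is medium, because the OPS and parts of the laboratory and derivation sections cannot be seen. This is a recommended improvement to a descriptive safety analysis; it does not threaten the trial's validity.

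**What to change.** Add the following to SAP 4.2.2.1:

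- For each assay, by dose and pooled placebo, report n/N. N is the number of participants negative at baseline, and n is the number of these who are positive at any post-baseline sample.
- Count unscheduled samples, including those prompted by symptoms under Protocol 8.2.8.
- Use the Table 2 cut-offs for the IgG assays and EBV VCA IgM. Use the reported positive/negative result for CMV IgM, VZV IgM and varicella. For EBV and CMV load, use a detection rule that the sponsor specifies in advance.
- Present the results as shift tables with a participant listing, and keep the continuous summaries for trends.
- If the OPS already holds these tables, a cross-reference in the SAP is enough.

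The cost is some SAP wording, a few shift tables and one listing, from data already collected and cut-offs mostly already written down. The drawback is more output with very wide intervals: 0/5 still allows up to 52.2%. The tables would describe cases and should not be read as estimating a rate.
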